6.1.2 Adverse Event Dictionary

AEs will be coded using MedDRA® (Medical Dictionary for Regulatory Activities) version 16.0 or higher. In MedDRA, each verbatim term is mapped to a preferred term and high level term (HLT), which is then mapped to a system organ class. Tables and listings will present data at the SOC and PT level.

6.1.3 Definition of Treatment-Emergent

Treatment-emergent adverse events are events that

- Began on or after the date of the first procedure.
- Had no recorded start date with a stop date after the first procedure.
- Had no recorded start date or stop date

For patients that received multiple treatments, treatment emergent adverse events will be attributed to the last treatment received.

Rules for date imputation to determine treatment emergent status can be found in Appendix C.

The Medical Dictionary for Regulatory Activities (MedDRA) dictionary will be used to classify all adverse events reported during the study by system organ class (SOC) and preferred term (PT). Adverse events will be summarized by SOC and PT.

Treatment Emergent adverse events by SOC, PT will be summarized and listed.

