- Optional assessments including Pentacam corneal tomography, corneal wavefront, optical coherence tomography (OCT), Brillouin microscopy, iTrace wavefront aberrometry/topography, Orbscan corneal topography, tomography, contrast sensitivity testing, or other non-invasive diagnostic tools that may be available to an investigator.

Interim visits may also be suggested in which similar safe non-invasive measurements may be obtained. Manifest refraction and non-contact corneal biomechanical and/or non-invasive biometry measurements may be obtained. These non-invasive measurements can be performed as frequently as the surgeon believes would be useful, especially in circumstances where the patient's vision and refraction can be expected to be changing rapidly.

Optional 1-2 month visit:

Some patients may experience significant changes in their refractive error, and may benefit from an optional visit at 1-2 months to get a new prescription for glasses or contact lenses.

Assessments:

- UCVA
- Slit lamp exam
- Pachymetry (ultrasound and/or Pentacam)
- Pentacam corneal tomography
- IOP

Optional Assessments:

- Optional assessments including corneal wavefront, optical coherence tomography (OCT), Brillouin microscopy, iTrace wavefront aberrometry/topography, Orbscan corneal topography, tomography, contrast sensitivity testing, or other non-invasive diagnostic tools that may be available to an investigator.
- Manifest refraction
- CDVA
- Medical and contact lens history will be recorded

Month 3 (60-120 days):

Assessments:

- UCVA
- Manifest refraction with CDVA
- Slit lamp exam (including rating of corneal haze if present from 0 (none) to 4)
- Pachymetry (ultrasound and/or Pentacam)
- Pentacam corneal tomography
- Medical and contact lens history will be recorded.
- IOP will be measured.

Optional Assessments:

- Quality of life and/or comfort survey questions.
- Optional assessments including corneal wavefront, optical coherence tomography (OCT), Brillouin microscopy, iTrace wavefront aberrometry/topography, Orbscan corneal topography, tomography, contrast sensitivity testing, or other non-invasive diagnostic tools that may be available to an investigator.

Month 6 (150-210 days):

Assessments:

- UCVA
- Manifest refraction with CDVA
- Slit lamp exam (including rating of corneal haze if present from 0 (none) to 4)
- Pachymetry (ultrasound and/or Pentacam)
- Pentacam corneal tomography
- Medical and contact lens history will be recorded.
- IOP will be measured.

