2.3 Unique Patient Identification

Patient number from the CRF does not uniquely identify individual patients. If a patient initially had bilateral treatment, then all data are captured under a single patient number. If a patient initially had unilateral treatment but subsequently had the procedure performed on the untreated eye, data for the newly treated eye were captured under a different patient number. If a patient completed the month 6 assessment and the investigator elected to perform the CXL procedure again, then all data for this repeated procedure are captured under a second patient number.

Sites will provide a list of paired patient numbers that can be used to map all data for each patient to be summarized appropriately.

Patients receiving subsequent CXL therapy were re-randomized. Therefore the subsequent treatment may differ from the initial randomized treatment given during the first procedure. Efficacy summarization will be by individual eye which can accommodate the differing treatments. Adjustments to the safety analysis will need to be considered since that is done overall rather than by individual eye.

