6. SAFETY

Safety data will be summarized using the safety population. Missing data will not be imputed for safety analyses. In the presence of partial dates, the available data (month and/or year) will be compared to the appropriate study reference dates to identify the most likely treatment received.

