8.3 Appendix C: Imputation Rules for Missing Dates

Incomplete diagnosis or treatment date

- If day is missing, day will be set to 15th of the month.
- If month and day are missing, month and day will be set to July 1st.
- If year and month and day are missing, date will be set to missing.

Adverse Event

- If onset date is completely missing, onset date is set to date of first treatment.
- If (year is present and month and day are missing) or (year and day are present and month is missing):
 - If year = year of first treatment, then set month and day to month and day of first treatment
 - If year < year of first treatment, then set month and day to December 31st.
 - If year > year of first treatment, then set month and day to January 1st.
- If month and year are present and day is missing:
 - If year=year of first treatment and month = month of first treatment then set day to day of first treatment date month < month of first treatment then set day to last day of month > month of first treatment then set day to first day of month
 - If year < year of first treatment then set day to last day of month
 - If year > year of first treatment then set day to first day of month
- For all other cases, set onset date to date of first treatment.

Concomitant Medications

- If start date is completely missing, start date will not be imputed.
- If (year is present and month and day are missing) or (year and day are present and month is missing), set month and day to January 1.
- If year and month are present and day is missing, set day to 1st day of month.
- If end date is completely missing, end date will not be imputed.
- If (year is present and month and day are missing) or (year and day are present and month is missing), set month and day to December 31.
- If year and month are present and day is missing, set day to last day of the month.

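### SAP 6.1.3 assigns a multiply treated patient's adverse events to the last UVA group received without regard to onset, so events before a second, re-randomised procedure are tabulated under a treatment not yet given

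*SAP*

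**What the plan says.** SAP 6.1.3 counts as treatment-emergent any event starting on or after the first procedure, and some events with no recorded start date. For patients with more than one procedure it adds: "For patients that received multiple treatments, treatment emergent adverse events will be attributed to the last treatment received". It refers to the date rules for one purpose only: "Rules for date imputation to determine treatment emergent status can be found in Appendix C".

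SAP 2.3 describes two routes to a later procedure: later treatment of an initially untreated eye, and a repeat procedure, introduced as "If a patient completed the month 6 assessment and the investigator elected to perform the CXL procedure again". It states "Patients receiving subsequent CXL therapy were re-randomized", that the later group may differ from the first, and that adjustments to the safety analysis will have to be considered. It specifies none.

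SAP 3.2.2 analyses safety by treatment actually received and lets an initially unilateral patient with a later procedure appear under more than one group. SAP 4.1 says something similar for a second eye treated in a different group.

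On dates, SAP 6 says "Missing data will not be imputed for safety analyses", but also that partial dates will be "compared to the appropriate study reference dates to identify the most likely treatment received". Appendix C says "If onset date is completely missing, onset date is set to date of first treatment".

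**The concern.** An adverse event cannot be caused by a procedure that has not yet happened. Under the sentence as written, a patient treated in Group 1 who has an event a month later and is then re-randomised to Group 2 has that event counted in Group 2.

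The interval exposed can be long. A repeat procedure follows the 6-month visit, whose window opens at day 150 in both Protocol 5.4 and Protocol Appendix 2. Events in roughly the first five months after the initial procedure therefore nominally precede the repeat. For second-eye treatment no interval is stated.

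The three groups differ only in UVA irradiance and exposure time. SAP 3.1 presents summaries by group so that treatments can be compared, and SAP 2.2 says the selected data support Phase 3 protocol development. What is at stake is the descriptive event rates by group in Tables 7.1 to 7.3. No between-group safety test is planned. Patients with a single procedure, or with initial bilateral treatment only, are unaffected.

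**Working it through.** The plan gives no figure on this point to reproduce. The check has three parts.

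**1. The rule applied to one hypothetical patient.** Group 1 on Day 1, Group 2 on Day 201.

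| Onset day | Rule as written | Last procedure on or before onset |
|---|---|---|
| 1, 30, 200 | Group 2 | Group 1 |
| 201, 250 | Group 2 | Group 2 |

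The two rules differ for every event before the second procedure whenever the second group differs from the first.

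**2. Whether other text repairs it.**
- SAP 6 compares dates with reference dates to find the likely treatment. That has a purpose only if dates decide attribution, but it covers partial dates only and does not qualify 6.1.3.
- For a wholly missing onset, 6.1.3 read literally gives the last group and Appendix C gives the first treatment date. However, 6.1.3 invokes Appendix C only for treatment-emergent status, and SAP 6 says safety data are not imputed.
- On denominators, neither SAP 3.2.2 nor 4.1 covers initially bilateral patients who are later re-treated.

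**3. Illustrative size.** All inputs are assumptions: equal allocation at each randomisation; per-procedure risks p = 10%, 20%, 20% in Groups 1, 2, 3; a share q having a second procedure, independent of prior events; all first-procedure events starting before the second procedure; one count per patient per column. Per patient initially assigned to group g:
- Denominator, both columns: 1 + 2q/3. Last column only: 1.
- Numerator by onset: p_g(1 + q) − q·p_g²/3.
- Numerator as written: (1 − q)p_g + (q/3)·Σ_a[1 − (1 − p_a)(1 − p_g)], summed over first groups a.
- Share of first-procedure events changing column: 2q/3.

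Worked at q = 0.4, both-column denominator 1.2667:
- By onset: Group 1 = 0.13867/1.2667 = 10.95%; Group 2 = 0.27467/1.2667 = 21.68%; difference 10.74 points.
- As written: Group 1 = (0.06 + 0.1333 × 0.75)/1.2667 = 12.63%; Group 2 = (0.12 + 0.1333 × 1.00)/1.2667 = 20.00%; difference 7.37 points. Loss = 1 − 7.37/10.74 = 31.4%.
- As written, last column only: 25.33% − 16.00% = 9.33 points. Loss 13.1%.

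Group 2 minus Group 1, in points, with the loss relative to the by-onset value:

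| q | By onset | Both columns (loss) | Last column only (loss) | Events moved |
|---|---|---|---|---|
| 2% | 10.05 | 9.84 (2.1%) | 9.97 (0.8%) | 1.3% |
| 5% | 10.11 | 9.60 (5.1%) | 9.92 (1.9%) | 3.3% |
| 10% | 10.22 | 9.22 (9.8%) | 9.83 (3.8%) | 6.7% |
| 20% | 10.41 | 8.53 (18.1%) | 9.67 (7.2%) | 13.3% |
| 30% | 10.58 | 7.92 (25.2%) | 9.50 (10.2%) | 20.0% |
| 40% | 10.74 | 7.37 (31.4%) | 9.33 (13.1%) | 26.7% |

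The by-onset value exceeds 10.0 because a patient with two procedures in the same group has two chances of an event but counts once. Against 10.0, the losses for q = 10–40% are 8–26% (both columns) and 2–7% (last only).

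Sensitivity, q = 10–40%:
- Patients with an event half as likely to be re-treated: both-column loss 6–18%. The last-column reading shows no shrinkage (10.3–11.3 points against 10.3–10.9 by onset).
- A quarter as likely: both-column loss 3.1–9.7%. Twice as likely: 15.1–49.0%.
- Rule read as last procedure before onset: loss 1–3% if 10% of first-procedure events start after the second procedure, 2–8% if 25% do.
- Equal risks, independent re-treatment: difference 0 under every reading.

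**The case against.** The strongest reply is that the last treatment received simply means the last one before the event. The partial-date sentence in SAP 6 supports that, since it would be pointless if the final treatment always took the event. On that reading little is lost: with the same inputs the Group 2 minus Group 1 difference is about 9.9 to 10.4 points, close to the assumed 10.0, and the proposed wording carries the same residual. SAP 2.3 also openly marks the safety analysis as needing adjustment.

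On size, the 10–31% figure needs the literal reading, both-column denominators, a doubled risk and a sizeable second-procedure share together, and the documents supply none of the rates or shares. Second-eye treatment may follow soon, in which case many first-eye events start after the second procedure and go to the second group under any onset rule. The analysis is interim and descriptive, and Listings 1 to 3 would allow moved events to be traced.

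Most of this stands as a limit on the size and on what can be said about intent. It does not rescue the sentence. SAP 6.1.3 is the only attribution rule given, it does not say before onset, and SAP 2.3 names the problem without solving it. A programmer following 6.1.3 would put events in the wrong column; the listings would help someone find them but would not correct the tables.

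**Conclusion.** The concern holds: the rule is wrong as written and should be fixed before the safety tables are run. The probable intent is attribution to the last procedure before onset, but the text does not say so and must be reconciled with SAP 6 and Appendix C. The number of events affected is unknown. The losses calculated above rest wholly on assumed allocation, risks and second-procedure shares; they show that the distortion could be material if second procedures are common and small if they are rare. Its direction also depends on how re-treatment relates to earlier events and on which denominator is used. The harm is confined to descriptive rates by group among patients with more than one procedure.

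**What to change.** Replace the sentence in SAP 6.1.3 with: *Each treatment-emergent adverse event will be attributed to the treatment given at the most recent procedure on or before its onset date.* Then:
- Define each column's denominator as patients with at least one procedure in that group, including initially bilateral patients who are later re-treated. Align SAP 3.2.2 and 4.1 with this, and apply the once-per-subject count of SAP 6.1.1 within column.
- State whether an onset date imputed under Appendix C also decides the group for events with missing or partial onset dates. Reconcile that with the no-imputation statement in SAP 6, and report how many such events there are.
- Optionally, add a sensitivity table by first treatment, limited to events before any second procedure.

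The cost is one sentence, one definition, a cross-reference and a little programming. Protocol 6.2 already requires onset dates, and SAP 2.3 already provides for the list of paired patient numbers. One limit remains: a late first-eye event starting after the second eye's procedure still goes to the second group, which is the 1–8% loss in the last-before-onset scenarios.

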3.2.2 Safety

The safety analysis set (SS) includes all subjects enrolled in the treated analysis set. Safety analysis will be performed using the Safety Analysis Set. Analysis of the SS will be performed by the treatment actually received as recorded on the CRF. Subjects with initial unilateral treatment that have a subsequent procedure may appear in the SS under different treatment groups if the subsequent treatment differs from the initial treatment.

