6.1 Treatment Emergent Adverse Events

6.1.1 General Considerations for Analysis of Adverse Events

General considerations for AE summaries and calculations are:

- Multiple events by preferred term (PT) and system organ class (SOC) will be counted once only per subject.

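### SAP 6.1.3 assigns adverse events of multiply treated patients to a treatment group with no onset condition, so read literally it can report an event under a regimen not yet given

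*SAP*

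**What the plan says.** SAP 6.1.3 anchors treatment-emergence to the first procedure. Its rule for patients with more than one procedure is: "For patients that received multiple treatments, treatment emergent adverse events will be attributed to the last treatment received".

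SAP 2.3 explains how a second procedure arises and how it is recorded. A patient first treated in one eye may later have the other eye treated, under a different patient number. An eye may also be treated again after Month 6, and "then all data for this repeated procedure are captured under a second patient number". In either case, "Patients receiving subsequent CXL therapy were re-randomized", and the SAP accepts that the second regimen may differ from the first. Sites supply a list of paired numbers so that each patient's data can be brought together. The section closes with an open item: "Adjustments to the safety analysis will need to be considered since that is done overall rather than by individual eye".

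Three other provisions bear on where an event is counted:

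- SAP 3.2.2, on the safety set: "Subjects with initial unilateral treatment that have a subsequent procedure may appear in the SS under different treatment groups", if the second regimen differs from the first.
- SAP 6.1.1, on counting: "Multiple events by preferred term (PT) and system organ class (SOC) will be counted once only per subject".
- SAP section 6, on dates: "In the presence of partial dates, the available data (month and/or year) will be compared to the appropriate study reference dates", in order to find the treatment most likely involved. For an onset with no date at all, SAP Appendix C says: "If onset date is completely missing, onset date is set to date of first treatment".

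**The concern.** UVA regimen is the randomised factor, and the SAP introduction says these interim analyses are meant to support the Phase 3 design and a meeting with FDA. Adverse-event tables by regimen are useful only if each event stands under a regimen the patient had already received when it began.

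The 6.1.3 sentence does not secure this. Events between the first and second procedures are treatment-emergent by definition, so they fall under the rule, and the rule points to the final procedure. If that procedure was in another group, the event moves to it. Several anticipated events in Protocol 6.3 are early reactions, for example an epithelial defect still open after 24 hours. A repeat in the same eye comes only after the 6-month visit, whose window opens at day 150 (Protocol 5.4). An early reaction to the first course would then be reported under a treatment given months later. For later treatment of the fellow eye, Protocol 4.1 sets no minimum gap.

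**Working it through.** The documents give no adverse-event rate, re-treatment rate or safety precision figure, so there is nothing to reproduce. The check is textual, followed by an illustration on assumed inputs.

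**Step 1: the provisions side by side**

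| Provision | What it settles | What it leaves open |
|---|---|---|
| SAP 6.1.3 | Group for events of multiply treated patients: the final treatment | Whether that treatment must precede onset |
| SAP 2.3 | Second regimen is randomised anew; numbers are linked per patient | The safety adjustment it says is needed |
| SAP 3.2.2 | Initially unilateral patients can appear in two groups | Same-eye repeats in patients first treated in both eyes |
| SAP 6 | Partial dates are compared with reference dates | Complete dates |
| SAP Appendix C | Fully missing onset becomes the first-treatment date | Which group follows from it |
| SAP 6.1.1 | One count per term per subject | Whether this is overall or per treatment column |

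The last two rows matter. An event with no onset date is dated to the first treatment by Appendix C and then, read literally, placed under the final treatment by 6.1.3.

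**Step 2: one patient followed through.** The dates are invented for the example. The right eye is treated in Group 1 on day 1. An epithelial defect begins on day 1 and has not healed by day 3. The left eye is treated in Group 2 on day 60.

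| | Group 1 | Group 2 |
|---|---|---|
| Patient in safety denominator (SAP 3.2.2) | yes | yes |
| Event, 6.1.3 read literally | 0 | 1 |
| Event, most recent procedure on or before onset | 1 | 0 |

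Had the second randomisation also given Group 1, both readings would agree.

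**Step 3: illustration of size.** Assumptions, none of them in the documents: 1:1:1 allocation at both randomisations; a share r of patients treated a second time, the same in every group; the same per-course risk at either course; first-course events beginning before the second procedure; re-treated patients in both denominators when the groups differ; and one count per patient per column.

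The second group differs from the first with probability 2/3, so the share of first-course events that change column is 2r/3:

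- r = 5%: 2 × 0.05 / 3 = 3.3%
- r = 10%: 6.7%
- r = 20%: 13.3%
- r = 30%: 20%

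With assumed per-course risks of 10%, 20% and 20% in Groups 1, 2 and 3, the Group 2 minus Group 1 difference in percentage points is:

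| r | Literal | By onset | Gap |
|---|---|---|---|
| 5% | 9.60 | 10.11 | 0.51 |
| 10% | 9.22 | 10.22 | 1.00 |
| 20% | 8.53 | 10.41 | 1.88 |
| 30% | 7.92 | 10.58 | 2.66 |

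For r = 10% and 1,000 first treatments per group, the Group 1 denominator is 900 + 5 × 33.33 = 1,066.7. The literal Group 1 count is 90 + 33.33 × (0.19 + 0.28 + 0.28) = 115, or 10.78%. By onset it is 90 + 33.33 × 0.19 + 2 × 66.67 × 0.10 = 109.7, or 10.28%. In Group 2 the two rates are 20.00% and 20.50%. Each group both loses and gains events. In this example the literal rule draws the groups together rather than lowering every rate.

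**The case against.** The strongest reply is that the literal reading fits the rest of the SAP poorly. Comparing partial dates with reference dates to find the likely treatment would be pointless if every event went to the final treatment regardless of date. A safety set analysed by treatment actually received, with patients allowed in more than one group, also fits attribution by onset. So does the disposition summary in SAP 4.1, which allows a subject in more than one column. First- and second-course events are recorded under different patient numbers, so moving an event would override how it was captured. The analysis is interim and descriptive.

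Much of this stands as evidence of intent, so a reader should not infer that events will in fact be misassigned. It does not close the gap. The date comparison covers partial dates only, the patient numbers are linked again before summarising, and 6.1.3 is the only attribution rule for a fully dated event.

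Two further inferences are tempting and not supported:

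- **Lost counts.** One might conclude that a term occurring after both treatments in different groups loses its first-group count because of 6.1.3. That holds only if the once-only rule works within each column. Read as written, per subject, it gives one count under either attribution. The SAP does not say which is meant.
- **Missing re-treatment split.** One might call it a defect that Tables 7.1 to 7.3 do not separate events after a same-eye repeat. This rests on table titles alone, since no shells are supplied, and Listings 2 and 3 allow tracing by hand. A split is a presentation choice.

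**Conclusion.** The point holds as a rule that is wrong if applied as written. For patients whose second regimen differs from their first, events that began between the two procedures would stand under a treatment not yet given. Those first treated in one eye could still count in the first group's denominator. Where both randomisations gave the same group, nothing changes.

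The size is unknown, because the documents give neither the number of re-treated patients nor event rates. The figures above show only how the effect would scale under the stated assumptions. Confidence is medium: the authors may mean the last treatment before onset, and the SAP cites protocol Version 4.3, which is not among the documents. The change is worth making on either view. If onset was intended, it records the intent. If not, it corrects the rule.

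**What to change.** In SAP 6.1.3, replace the attribution sentence with three provisions:

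1. Attribute each event to the most recent procedure on or before its onset, both for same-eye repeats and for later fellow-eye treatment.
2. If the onset date is fully missing, use the patient number under which the event was recorded (SAP 2.3). Use the Appendix C first-treatment default only if that does not settle it.
3. State that the once-only count in SAP 6.1.1 applies within each treatment column, so a term that occurs under two groups counts once in each.

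The cost is a few sentences and the matching programming. Procedure dates, onset dates and the paired-number list are already provided for.

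The remaining weakness is late events. Dry eye beyond 3 months, scarring or progression in a first-treated eye would still go to the second group if it began after fellow-eye treatment. Only the affected eye, if the CRF records it, would resolve this. Protocol 6.2 does not list eye among the event characteristics.

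Optionally, report the number of patients with a same-eye repeat and show events after the repeat separately. That group may be too small to say much.
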